# Study protocol

## Background

Adhesion formation after surgical operations in abdomen and pelvis is the most common cause for long-term postoperative complications. These adhesions can have various consequences like adhesive small bowel obstruction, need for adhesiolysis in future operations, chronic abdominal pain, secondary infertility (1). Adhesive small bowel obstruction (ASBO) is the most common pathology of the small bowel and frequently results in surgical emergencies (2). Formation of adhesions can begin within a few hours after an operation (3). Characteristics of ASBO is the presence of abdominal pain, vomiting, distention, and obstipation in conjunction of confirmatory imaging (4). In the UK small bowel obstruction accounted for 51% of all emergency laparotomies (5). Scott et al. recently published on 7 emergency surgery procedures counting for 80% of morbidity and death related to emergency surgery (6). ASBO was the most common diagnosis for both the top-2 and top-5 procedure in this list.

The incidence of small bowel obstruction following peritoneal surgery is estimated between 9% to 15%, with adhesions being the most common cause of SBO, accounting for almost 60% of all cases of bowel obstruction (7). Approximately 20-30% of cases requires a reoperation to resolve ASBO.

Remarkably, little is known about the optimal management of ASBO, despite the huge morbidity and economic burden of ASBO (8). The World Society for Emergency Surgery published a consensus guideline for Diagnosis and Management of adhesive small bowel syndrome. These guidelines are not universally implemented and their recommendations are based on low quality evidence and sometimes conflicting literature (9). Diagnosis and treatment of ASBO therefore often depend on surgeon's preferences rather than evidence based medicine.

In this nationwide audit we will study differences in the management and outcomes of patients admitted with ASBO to surgical emergencies units in the Netherlands. By analysing these differences we hope to learn from best practices, and define new research questions to improve the diagnosis and treatment of ASBO.

## Purpose and Research Question

In this research the differences in the management and outcomes will be studied from patients admitted with ASBO to surgical emergencies units in the Netherlands. The research question is:

*"What is the impact of different variations in management and treatment of adhesive small bowel obstruction in the Netherlands on patient outcomes?"*

A nationwide cohort is being observed over a short period of time, to answer the following four defined questions.

1. How many patients in the Netherlands presenting with adhesive small bowel obstruction have a CT-scan in their diagnostic work-up? And in how many patients does CT-scan impact initial management of ASBO (i.e. different cause of SBO found, or conservative trial vs. direct surgery)?
2. How long do Dutch surgeons continue a conservative trial in patients with persistent obstruction who are not clinically deteriorating?

3. Does continuing a conservative trial for more than 72 hours adverse impact final outcomes?
4. How many patients that are surgically treated for ASBO in the Netherlands have laparoscopic surgery and what are the outcomes of laparoscopic surgery?

The analysis of these defined questions will offer insights in how differences in management can impact outcome. Further, the data will also be used to generate new hypotheses on best practice in management of ASBO.

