## Plan of investigation

The study design of this study is a prospective observational cohort study. We will use a snapshot study design, to include a large cohort of patients with a clinical suspicion of ASBO over a period of 6 months. This design has previously been used in the Dutch surgical society to gather data of a large group of patients over a short period of time (10). We will include as many patients as possible with a clinical suspicion of ASBO over a period of 6 months. We will contact every hospital in our country with an informative letter about our research. When the hospital accepts to participate in the collaborative study group, a digital snapshot questionnaire will be sent to provide hospital characteristics and patient data about symptoms, diagnosis, imaging, risk factors and treatment. The questionnaires will be filled by local collaborating research partners, for each patient with a suspicion of ASBO. The questions will be clear and easy to fill in. Therefore it is not a big threshold for the hospitals to participate and a lot of information can be received.

The database will be finished in Castor, in which the questionnaires will be filled in. We aim to include 500 patients with ASBO over 6 months of time. Our analysis will include regression analysis for variation in clinical management and outcome of ASBO treatment. The results will be used to form new hypotheses and update guidelines on management of ASBO.

The METC of the Radboudumc has given approval for this study. This study is not WMO- compulsory.

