## Data and statistical analysis

Baseline data consisted of patients age, sex, Charlson comorbidity index, ASA classification and the number of previous abdominal operations. Categorical data will be analysed using a Chi-square or Fisher's exact test, as appropriate. Continuous data will be analysed using independent t-test or Mann-Whitney U test if not normal distributed. Continuous variables are presented as means with standard deviation, or medians with interquartile range (25–75) if non-normal distribution. Dichotomous or categorical variables are presented as absolute numbers and percentages.  $P < 0.05$  was considered significant. All analyses will be performed using SPSS version 23.0 (Armonk, NY: IBM Corp).

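### Questions 2 and 3 do not separate a conservative trial with surgery in reserve from non-operative care in patients for whom surgery was ruled out

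*Combined protocol and SAP*

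**What the plan says.** Under Purpose and Research Question, question 2 concerns duration: "How long do Dutch surgeons continue a conservative trial in patients with persistent obstruction who are not clinically deteriorating". Question 3 concerns consequence: "Does continuing a conservative trial for more than 72 hours adverse impact final outcomes". Question 3 does not repeat question 2's restriction to stable patients who remain obstructed. The only other use of the term is in question 1, where the example of a change in initial management is "conservative trial vs. direct surgery". The protocol gives no definition of a conservative trial, and it names no third category for non-operative care with surgery ruled out.

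The Plan of investigation sets the entry rule: "We will include as many patients as possible with a clinical suspicion of ASBO over a period of 6 months". No exclusion is stated for patients who decline surgery or are judged unfit for it. Besides hospital characteristics, the questionnaire is to collect "patient data about symptoms, diagnosis, imaging, risk factors and treatment". The questionnaire itself is not reproduced.

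Under Data and statistical analysis, "Baseline data consisted of patients age, sex, Charlson comorbidity index, ASA classification and the number of previous abdominal operations". The tests named there are unadjusted: "Categorical data will be analysed using a Chi-square or Fisher's exact test, as appropriate", with a t-test or Mann-Whitney test for continuous data. The Plan of investigation adds that "Our analysis will include regression analysis for variation in clinical management and outcome of ASBO treatment", but names no outcome, model or covariate.

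**The concern.** In ordinary use, a trial of conservative treatment implies that an operation follows if it fails. Some patients admitted with suspected adhesive small bowel obstruction (ASBO) have no such next step: they have declined surgery, are unfit for it, or have a treatment limitation. Question 2 is about a surgeon's decision on when to stop waiting, and for these patients there is no such decision. In question 3, their outcomes would be credited to the length of the wait although no earlier operation was on offer. That is confounding by indication.

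The restriction in question 2 does not remove them, since a patient without a surgical option can be obstructed and stable. Age, Charlson index and ASA class are related to fitness, but they do not record a refusal or a treatment limitation, so adjusting for them would help only in part.

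The stakes follow from the stated use of the results, which includes updating ASBO guidelines. A spurious association at 72 hours, in either direction, could carry into guidance.

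**Working it through.** **What the plan's own figures give.** The plan states no figure on this point. Its target of 500 patients has no derivation to reproduce. The Background says 20-30% of cases need reoperation. Applied to 500, that is 100-150 operated and 350-400 not operated. The non-operated majority is where the two kinds of patient would be mixed, but nothing in the documents says in what proportion.

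**Question 3: mortality comparison.** All inputs below are assumptions, and mortality stands in for the undefined final outcomes.
- p: mortality of surgical candidates, the same either side of 72 h, so the true risk ratio is 1 (2% or 4%)
- q: mortality of patients with surgery ruled out (20% or 40%)
- f: share of such patients in a duration group

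Group mortality = p(1 − f) + q·f.

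| p, q | f beyond 72 h / at or before | Mortality beyond 72 h | Mortality at or before | Risk ratio |
|---|---|---|---|---|
| 4%, 20% | 5% / 1% | 0.04×0.95 + 0.20×0.05 = 4.8% | 0.04×0.99 + 0.20×0.01 = 4.2% | 1.15 |
| 2%, 40% | 10% / 2% | 0.02×0.90 + 0.40×0.10 = 5.8% | 0.02×0.98 + 0.40×0.02 = 2.8% | 2.10 |
| 2%, 40% | 15% / 3% | 0.02×0.85 + 0.40×0.15 = 7.7% | 0.02×0.97 + 0.40×0.03 = 3.1% | 2.45 |
| any | 5% / 5% | equal | equal | 1.00 |
| 4%, 20% | 1% / 5% | 4.2% | 4.8% | 0.87 |
| 2%, 40% | 2% / 10% | 2.8% | 5.8% | 0.48 |

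Across the four combinations of p and q, the ratio runs from 1.15 to 2.45 when these patients concentrate beyond 72 h (5-15% against 1-3%). It runs from 0.48 to 0.87 when they concentrate at or before 72 h (1-2% against 5-10%). Where they fall decides the sign.

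**Question 2: duration.** Mean = m(1 − f) + d·f, so the shift is (d − m)·f, with m the candidates' mean, d that of the others, and f from 2% to 10% (all assumed).
- m = 72 h, d = 168 h: shift 96×0.02 = +1.9 h to 96×0.10 = +9.6 h
- m = 48 h, d = 168 h, f = 10%: 120×0.10 = +12.0 h, the largest case tried
- m = 72 h, d = 36 h: shift −36×0.02 = −0.7 h to −36×0.10 = −3.6 h

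For the median, take a two-part log-normal mixture (sigma 0.7, candidate median 60 h). If the others have a median of 144 h, the overall median becomes 60.8-64.5 h, and the share above 72 h rises from 39.7% to 40.6-44.1%. If their median is 36 h, the overall median becomes 59.4-57.2 h.

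**Which direction is likelier.** A candidate's non-operative course can end by resolution or by operation. Without a surgical option the second exit is closed, which tends to lengthen the course among patients who remain obstructed and stable. Question 2's restriction should also remove most early deaths, because those patients deteriorate. Question 3 does not carry that restriction, so early deaths can enter its shorter-duration group.

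**The case against.** Four stronger readings are tempting, and the documents support none of them.

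- **A reader might infer that the plan counts every long non-operative course as a conservative trial.** No section says so. The word trial, the contrast with direct surgery in question 1 and the restriction in question 2 all point to a narrower group. What stands is that no definition, exclusion or analysis rule enforces the narrower meaning.
- **A reader might infer that these patients are certain to go unidentified.** The questionnaire is not in the documents. Its published description gives broad domains, not items, and omits outcomes, which must be collected for questions 3 and 4. The treatment domain could hold a suitable item. Even so, no rule for using it appears in the analysis section.
- **A reader might infer that both results are inflated.** Early death or early discharge to palliative care would place these patients at or before 72 h and reverse the bias. If question 2 were measured only as time to operation in operated patients, they would drop out of it altogether. The plan does not say which measure is meant.
- **A reader might take the worst case as the expected size.** With 3.5% mortality in candidates, 50% in the others and all of the others beyond 72 h, shares of 5%, 10% and 15% give 5.8%, 8.2% and 10.5%, or ratios of 1.7, 2.3 and 3.0. That fixes by assumption the allocation that determines the sign, so it is an upper-side scenario.

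It is also fair to say that ASA, Charlson and age permit partial adjustment if the announced regression uses them. No model is specified, so this reduces the concern without removing it.

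**Conclusion.** The point holds in limited form. As written, questions 2 and 3 do not distinguish patients with surgery in reserve from patients for whom it was ruled out, and the named data visibly identify neither group. Both answers may be biased. Upward is the likelier direction because there is no operative exit and the prognosis is probably worse; downward is possible if many of these patients die or leave early.

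For question 3, the apparent mortality risk ratio under no true effect spans about 0.48 to 2.45 over the assumed inputs. For question 2, the median moves only a few hours and the mean somewhat more. These figures rest on assumed mortalities, shares and durations, and show sensitivity, not an estimate for this cohort.

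This is more than missing detail and should be corrected. If the information is not collected prospectively, central analysts cannot recover it from coded data. The hospitals hold the keys, and going back to the notes later would be slower and open to hindsight.

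**What to change.** 1. Check the questionnaire. If it has no such item, add one to Castor, recorded as of admission for every patient: *Was surgery an available option if conservative treatment failed? Yes / no, patient declined / no, unfit or treatment limitation.*
2. State that the main analysis of questions 2 and 3 is restricted to patients answered yes. Use admission status only, with the same rule for both duration groups. A status taken at 72 h would not work, because patients whose conservative course ended sooner have none. Reclassifying by later decisions would let the course itself determine who is analysed.
3. Report the remaining patients separately, with their number and outcomes.
4. Show the unrestricted result as a sensitivity analysis.

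The cost is one extra item, a short statement of the analysis set, and a somewhat smaller set for questions 2 and 3. The documents do not allow the reduction to be sized. Two limits remain. Patients in whom surgery is ruled out after admission stay in the main set, and the restriction does not deal with other confounding of the 72-hour comparison, for which the regression covariates still need to be named.

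### Question 3 names no comparator or outcome and does not restate question 2's population; comparing trials beyond 72 h with all other conservatively treated patients could mislead in either direction

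*Combined protocol and SAP*

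**What the plan says.** In the combined protocol and SAP, Purpose and Research Question lists four defined questions. Question 2 asks: "How long do Dutch surgeons continue a conservative trial in patients with persistent obstruction who are not clinically deteriorating". Question 3 follows: "Does continuing a conservative trial for more than 72 hours adverse impact final outcomes". The limit on population appears in question 2 only. Question 3 gives the exposure but not the group it is compared with, and no section defines the outcomes.

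Data and statistical analysis states: "Baseline data consisted of patients age, sex, Charlson comorbidity index, ASA classification and the number of previous abdominal operations". The only tests specified are unadjusted two-group tests, for example "Categorical data will be analysed using a Chi-square or Fisher's exact test, as appropriate", with the t-test or Mann-Whitney test for continuous data. Plan of investigation adds: "Our analysis will include regression analysis for variation in clinical management and outcome of ASBO treatment". It gives no model, covariates or time origin. The same section says: "The results will be used to form new hypotheses and update guidelines on management of ASBO".

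**The concern.** Length of a conservative trial is not fixed at admission. A patient enters the group beyond 72 h only by being neither resolved nor operated on at 72 h. If everyone else treated conservatively is the comparator, that group pools patients who resolved early (good prognosis), patients who deteriorated early (poor prognosis) and patients operated on early by choice. The contrast then partly measures the course of the disease, not the effect of waiting.

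Age, sex, Charlson index, ASA class and previous operations are known at admission. They cannot remove a difference created afterwards unless they fully determine the course. If length of stay from admission is an outcome (the plan does not say), every patient beyond 72 h has a stay of more than 72 h by definition, and the comparator has no such floor.

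The study is mainly a hypothesis-generating audit, but its results are also meant to inform guidelines. An unaligned comparison could show harm from waiting where there is none, or hide a real harm.

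**Working it through.** **No figure to reproduce.** The target of 500 patients comes with no event rate, effect size or power. The one relevant rate is in Background: about 20-30% of cases are operated on, with no split by time. Every other input below is an assumption.

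**What is fixed for question 3**

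| Element | Plan |
|---|---|
| Exposure | Conservative trial beyond 72 h |
| Comparator | Not stated |
| Population | Restriction in question 2 only |
| Outcome | Not defined |
| Time origin | Implied (trial start); recording not described |
| Adjustment | Regression without model or covariates |

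**Worked example, no harm from waiting built in.** Of 400 patients starting conservatively, by 72 h 60% resolve and 15% are operated on; half of the remaining 100 are operated on later. Operated on in all: (60 + 50)/400 = 27.5%. Complication risk is 5% if resolved, 40% after early surgery (which includes deteriorated patients) and 30% after late surgery.

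- Beyond 72 h: 0.5 × 30% + 0.5 × 5% = 17.5%.
- All others: (60 × 5% + 15 × 40%)/75 = 12.0%. Risk ratio 17.5/12.0 = 1.46; P<0.05 in 29% of simulated studies (100 v 300 patients, two-sided).
- With 30% risk for early surgery too: (60 × 5% + 15 × 30%)/75 = 10.0%. Risk ratio 1.75; P<0.05 in 51%.

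**The sign is not fixed.** The inputs were varied: 55-85% resolved and 2.5-20% operated on by 72 h; at least 10% left, of whom 20-70% are operated on later; 0-15% direct surgery; risks 3-5% (resolved), 30-45% (early surgery) and 30% (late surgery). Combinations were kept only if 20-30% were operated on overall. The extremes are:

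- Lowest: 55% resolve, 20% operated on by 72 h, 25% left, 20% of these later. Beyond 72 h: 0.2 × 30% + 0.8 × 3% = 8.4%. Others: (55 × 3% + 20 × 45%)/75 = 14.2%. Risk ratio 0.59. Operated on: 20% + 0.2 × 25% = 25%.
- Highest: 85% resolve, 2.5% operated on by 72 h, 12.5% left, 70% of these later. Beyond 72 h: 0.7 × 30% + 0.3 × 3% = 21.9%. Others: (85 × 3% + 2.5 × 30%)/87.5 = 3.8%. Risk ratio 5.8. With 15% direct surgery, operated on: 15% + 0.85 × (2.5% + 0.7 × 12.5%) = 24.6%.

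**Does baseline adjustment help?** A simulation of 3,000 studies of 400 had risk depend on course and a baseline score (log OR 0.4), never on timing. Of 400 patients, 240 resolve by 72 h (5%), 32 deteriorate and are operated on (40%) and 128 persist without deteriorating (17.5%). Of the 128, 28 are operated on before 72 h by choice, 30 at 72 h, and 70 continue. By hand, the others' risk is (240 × 5% + 32 × 40% + 58 × 17.5%)/330 = 10.6%, so the risk ratio is 17.5/10.6 = 1.65. The simulation gave:

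- Continuing v all others, crude: RR 1.66, P<0.05 in 39%.
- The same, adjusted for baseline: OR 1.82, P<0.05 in 39%.
- 72 h landmark, continuing v surgery at 72 h among the 100 still obstructed and stable: OR 1.01, P<0.05 in 4%.

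A separate model with 500 patients and two baseline covariates, also with no timing effect, gave adjusted ORs of 2.10, 1.60 and 0.58 in three scenarios. Restricting to persistent, stable patients gave 0.99-1.00. The 0.58 scenario has about 42% deteriorating early, above the Background range, so the 0.59 example above is the better evidence on sign.

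**The landmark is not a cure.** If clinical state at 72 h drives both surgery (log OR 1.0) and outcome (log OR 0.8), the landmark adjusted for baseline alone gives OR 0.54 for continuing (P<0.05 in 23%). Adding that state gives 1.02 (5%).

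**Precision after restriction.** Narrower ranges (55-65% resolved, 10-20% operated on by 72 h) leave 60 to 140 of 400 patients. With 20% risk, the 95% CI half-width is 1.96 × √(0.16/n₁ + 0.16/n₂):

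| Split | 60 patients | 140 patients |
|---|---|---|
| 50/50 | ±20 points | ±13 points |
| 20/80 | ±25 points | ±17 points |
| 10/90 | ±34 points | ±22 points |

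Events number 0.2 × 60 = 12 to 0.2 × 140 = 28. Exposure plus six covariates is seven parameters, or about 2 to 4 events each.

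**The case against.** The strongest reply is that the biased comparison is supposed, not planned. A reader might infer that the study will compare trials beyond 72 h with everyone else; no section says so. Question 3 follows question 2, and a patient whose obstruction has resolved has no trial to continue, so inheriting question 2's population is a natural reading. That stands, and makes the bias conditional. It does not supply a comparator, outcome or time origin, and nothing in the analysis section settles the reading.

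A reader might also infer that the needed data are not collected. The documents do not support that. The questionnaire is not included, question 2 cannot be answered without trial duration, and Plan of investigation lists "patient data about symptoms, diagnosis, imaging, risk factors and treatment". Regression covariates therefore need not stop at the five baseline variables. The fair statement is that event times and state at 72 h are not confirmed.

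The rates are assumed. If the 400 were part of the target of 500 and the other 100 had direct surgery, (110 + 100)/500 = 42% would be operated on, above the Background range. The rejection rates are therefore illustrations.

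Finally, a landmark narrows the question, cannot carry many covariates, and needs a decision window. Patients who resolve inside that window would count as continuing and flatter it. All of this stands and shapes the fix.

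**Conclusion.** The point holds in conditional form and should be fixed before analysis. Question 3 lacks a comparator, an outcome and an explicit population. If the stated methods compare more than 72 h with all other conservatively treated patients, the answer can be biased, and admission variables do not remove the bias. This goes beyond missing detail, because the only tests specified, applied to the exposure as worded, allow that comparison in a question meant to inform guidelines.

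Size and direction are unknown. A reader might infer from the worked example that the study would falsely show harm from waiting, or that 29-51% is its false-positive rate. Neither follows: the documents give no event rates, and assumed inputs within the 20-30% operated on give risk ratios on both sides of 1. What does not depend on the assumed rates is that the groups are formed after admission.

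**What to change.** State that question 3 applies to question 2's population, count time from the start of the conservative trial, and name the outcomes. Do not compare trials beyond 72 h with patients who had already resolved or deteriorated by 72 h. Then choose one analysis that aligns the time origin:

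- **72 h landmark** among patients still obstructed and not deteriorated, comparing surgery within a stated window with continuing. Later surgery counts as continuing. Count outcomes and length of stay from 72 h, and say how resolution inside the window is handled so that it does not favour continuing.
- **Time-dependent exposure** from trial start, if earlier surgery in stable patients belongs to the intended contrast.

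Adjust for a few prespecified covariates only, including clinical state at 72 h where recorded, because events will be few. Report the effect with a 95% CI, do not read P≥0.05 as no adverse impact, and state that confounding by indication remains.

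Cost: wording only, if times of trial start, resolution, deterioration and surgery, and state at 72 h, are already recorded; otherwise added questionnaire fields. The landmark is an ordinary regression that fits the existing software plan ("All analyses will be performed using SPSS version 23.0"), at the price of fewer patients and wide intervals. The time-dependent option keeps more patients but needs every event time and a more complex model.
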